5.1.2.2 Statistical Methods

- For each of the non-inferiority hypotheses (hypothesis 1 to 5, 9 to 12 and 14 to 16) using the percentage rates (eg, vaccine response rate), the CI of the difference in proportions will be computed using the Wilson Score method without continuity correction (15).

Let $\hat{\theta} = p_1 - p_2$, then $L = \hat{\theta} - \delta$ and $U = \hat{\theta} + \varepsilon$ are respectively the lower and the upper limits of the CI, where:

$$\delta = Z_{0.025} \sqrt{\left\{ \frac{l_1(1-l_1)}{n_1} + \frac{u_2(1-u_2)}{n_2} \right\}}$$

$$\varepsilon = Z_{0.025} \sqrt{\left\{ \frac{l_2(1-l_2)}{n_2} + \frac{u_1(1-u_1)}{n_1} \right\}}$$

l_1 and u_1 are calculated from the CI of the single proportion in Group I given by:

$$\frac{(2n_1p_1 + Z_{0.025}^2 \pm Z_{0.025} \sqrt{(Z_{0.025}^2 + 4n_1p_1(1-p_1))})}{2(n_1 + Z_{0.025}^2)}$$

l_2 and u_2 are calculated from the CI of the single proportion in Group II given by:

$$\frac{(2n_2p_2 + Z_{0.025}^2 \pm Z_{0.025} \sqrt{(Z_{0.025}^2 + 4n_2p_2(1-p_2))})}{2(n_2 + Z_{0.025}^2)}$$

where $Z_{0.025}$ is the upper 97.5th percentile of the standard normal distribution.

where Group I and Group II above refer to Group 1a and Group 2a, Subgroup 1 and 2, or Subgroup 1b and 2b respectively for corresponding hypotheses.

- For each of the non-inferiority hypotheses (hypothesis 6 to 8 and 13) using the GMC ratios, the statistical methodology will be based on the use of the 2-sided 95% CI of difference in means of post-vaccination Log10 transformed concentrations between Group 1 and Group 2 or between Subgroup 1a and Subgroup 2a with normal approximation. Logarithm transformation of the individual post-vaccination concentrations will be calculated. Assuming that Log₁₀ transformation of the data is normally distributed, the 95% CI for the difference in Log₁₀(GMC) between two groups will be in the form:

$$\bar{X}_i - \bar{X}_j \pm t(1 - \alpha/2, n_i + n_j - 2) \cdot S \sqrt{1/n_i + 1/n_j}$$

where $\bar{X}_i = \log_{10}(\text{GMC})$ is the mean of $\log_{10}(\text{concentration})$ of Group i ,

$S^2 = [(n_i - 1) S_i^2 + (n_j - 1) S_j^2] / (n_i + n_j - 2)$ is the pooled sample variance,

n_i and S_i^2 are the sample size and sample variance of Group i ,

$t(1 - \alpha/2, n_i + n_j - 2)$ is the 100(1- $\alpha/2$) percentile of the t -distribution with degrees of freedom $df = n_i + n_j - 2$.

The 95% CI for the GMC ratios between Group 1 and Group 2 or between Subgroup 1a and Subgroup 2a will be formed by taking the antilogarithms of the lower and upper limits of the 95% CI for the difference in $\log_{10}(\text{GMC})$ between both vaccine groups.

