### 5.2.6 Medical History

Prior to enrollment, subjects will be assessed for pre-existing conditions and illnesses, both past and ongoing. Any such conditions will be documented in the source document. Significant medical history (reported as diagnosis) including conditions for which the subject is or has been followed by a physician or conditions that could resume during the course of the study or lead to an SAE or to a repetitive outpatient care will be collected in the CRB. The significant medical history section of the CRB contains a core list of body systems and disorders that could be used to prompt comprehensive reporting, as well as space for the reporting of specific conditions and illnesses.

---

a The components of all study vaccines are listed in Section 6.1.1 and in the Investigator's Brochure

For each condition, the data collected will be limited to:

- Diagnosis (this is preferable to reporting signs and symptoms)
- Presence or absence of the condition at enrollment

The reporting of signs and symptoms in lieu of a diagnosis is strongly discouraged.

Dates, medications, and body systems are not to be recorded, and the information collected will not be coded. Its purpose is to assist in the later interpretation of safety data collected during the trial.

In addition, maternal immunization history will be collected in the CRB as follows:

- Tdap vaccination received during pregnancy with the subject enrolled in the study and date of vaccination
- Any meningococcal vaccination received at any time (name or type of meningococcal vaccine, i.e. Menactra, meningococcal ACWY conjugate vaccine, meningococcal B vaccine, etc.) and date of vaccination

The information collected will not be coded. This information will further assist with the interpretation of data collected during the trial.

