3.1 Study Design

This study will be a Phase III, partially modified double-blind, randomized, parallel-group, active-controlled, multi-center study to compare the immunogenicity and safety of MenACYW conjugate vaccine and MENVEO® (Meningococcal [Groups A, C, Y, and W-135] Oligosaccharide Diphtheria CRM₁₉₇ Conjugate Vaccine) when administered concomitantly with routine pediatric vaccines to healthy infants and toddlers in the US.

Approximately 2628 healthy infants aged ≥ 42 to ≤ 89 days will be randomized 2:1 to the following 2 groups:

- **Group 1 (G1):** MenACYW conjugate vaccine and routine vaccines
- **Group 2 (G2):** MENVEO® and routine vaccines

Each group will be further randomized 2:1 in 2 subgroups based on the time of analyses conducted in the 2nd year of life (30 days after the 12-month vaccination or 30 days after the 15-month vaccination, respectively):

- **Group 1:**
 - **Subgroup 1a (G1a)** (12 months): MenACYW conjugate vaccine and routine vaccines at 2, 4, 6, and 12 to 15 months of age
 - **Subgroup 1b (G1b)** (15 months): MenACYW conjugate vaccine at 2, 4, 6, and 15 to 18 months of age and routine vaccines at 2, 4, 6, 12 to 15 months of age, and 15 to 18 months of age
- **Group 2:**
 - **Subgroup 2a (G2a)** (12 months): MENVEO® at 2, 4, 6, and 12 months of age and routine vaccines at 2, 4, 6, 12, and 15 to 18 months of age
 - **Subgroup 2b (G2b)** (15 months): MENVEO® at 2, 4, 6, and 12 months of age and routine vaccines at 2, 4, 6, 12, and 15 to 18 months of age

To be specific, the time of analyses as well as the collection of blood samples conducted in the 2nd year of life for Subgroup 1a and 2a is 30 days after the 12-month vaccination. The time for Subgroup 1b and 2b is 30 days after the 15-month vaccination. The schedule of vaccination and blood sampling is further detailed in [Table 3.1](#).

All subjects will receive the following routine vaccines as per the ACIP recommendations (see [Table 3.1](#)).

- Pentacel® (diphtheria, tetanus, pertussis [acellular, component]-poliovirus [inactivated]//*Haemophilus influenzae* type b [DTaP-IPV//Hib]) at 2, 4, 6, and 15 to 18^a months of age
- Prevnar 13® (pneumococcal 13-valent conjugate vaccine [PCV13]) at 2, 4, 6, and 12 to 15 months of age
- RotaTeq® (pentavalent rotavirus vaccine [RV5]) at 2, 4, and 6 months of age
- ENGERIX-B® (HB vaccine) at 2 and 6 months of age^b
- M-M-R® II (measles, mumps, rubella [MMR] vaccine) at 12 to 15 months of age

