The DTaP (Diphtheria, Tetanus, and Pertussis) ECL (electrochemiluminescent) is a multiplexed serological assay which allows for the simultaneous quantification of human antibodies to 6 specific antigens including diphtheria toxoid, tetanus toxoid, and 4 pertussis antigens: PT, FHA, FIM and PRN. In this assay, each well of a 96-well microtiter plate is pre-coated in precise positions with the 6 different antigens in a multi-spot fashion. Following incubation with serum samples, antigen-specific antibodies bind to the respective antigens. The captured antibodies are then detected using a sulfotag conjugated anti-human IgG conjugate. Electrical stimulation of the conjugate in the presence of a chemiluminescent substrate results in the generation of a light signal from each specific spot that is captured by a camera in relative light units. The signal generated is directly proportional to the amount of antibodies present in the sample, which is quantified using software and based on an established reference standard sample curve. The LLOQ for Diphtheria is 0.005 IU/mL, the LLOQ for Tetanus is 0.01 IU/mL and the LLOQ for Pertussis antigens is 2.00 EU/mL.

This method will be performed on BL1 and BL2 collected from all groups, and BL3 and BL4 collected from Subgroups 1b and 2b.

Anti-Hepatitis B Antibodies

Anti-HB surface antibodies (anti-HBs) will be measured by the commercially available VITROS ECi/ECiQ Immunodiagnostic System using chemiluminescence detection technology. The VITROS ECi Immunodiagnostic system uses an antibody-mediated antigen sandwich formation to detect the presence of anti-HBs total immunoglobulin in human serum. This involves the reaction of anti-HBs in the sample with plasma-derived HBsAg (ad and ay subtypes) coated onto the wells. A horseradish peroxidase (HRP)-labeled HBsAg conjugate (ad and ay subtypes) then complexes with the bound anti-HBs forming an antigen sandwich. Substrate is then added which catalyzes HRP, producing light. The light signals are read by the VITROS ECi/ECiQ. Immunodiagnostic System and the amount of HRP conjugate bound is directly proportional to the concentration of anti-HBs present in the sample. Results are reported in mIU/mL by comparison to a calibrator provided by the manufacturer that has been calibrated according to the World Health Organization (WHO) First International Reference Preparation for Antibody to HBsAg (1977). The LLOQ is 5 mIU/mL.

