Thirty days after the 6-month Pentacel® vaccination, the percentages of subjects who achieve $\geq 1:8$ in anti-polio antibody titers (type 1, type 2, and type 3) in Group 1 are non-inferior to those in Group 2.

Null hypothesis (H0): $p(\text{pol, G1}) - p(\text{pol, G2}) \leq - 5\%$

Alternative hypothesis (H1): $p(\text{pol, G1}) - p(\text{pol, G2}) > -5\%$
where $p(\text{pol, G1})$ and $p(\text{pol, G2})$ are the percentages of subjects in Group 1 and Group 2, respectively, who achieve $\geq 1:8$ in anti-polio antibody titers (type 1, type 2, and type 3). Each of the antigens of type 1, type 2, and type 3 will be tested separately. If the lower limit of the 2-sided 95% CI of the difference between the 2 proportions is $> -5\%$ for each type, the inferiority assumption will be rejected.

- **Secondary Hypothesis 5 (Anti- rotavirus % \geq 3-fold rise)**

Thirty days after the 6-month rotavirus vaccine administration, the percentages of subjects who achieve ≥ 3 -fold rise in serum IgA antibody concentrations against the rotavirus in Group 1 is non-inferior to those in Group 2.

Null hypothesis (H0): $p(\text{rota, G1}) - p(\text{rota, G2}) \leq -10\%$

Alternative hypothesis (H1): $p(\text{rota, G1}) - p(\text{rota, G2}) > -10\%$
where $p(\text{rota, G1})$ and $p(\text{rota, G2})$ are the percentages of subjects in Group 1 and Group 2, respectively, who achieve ≥ 3 -fold rise in serum anti-rotavirus IgA antibody concentrations (serotypes G1, G2, G3, G4, and P1A[8]). If the lower limit of the 2-sided 95% CI of the difference between the 2 proportions is $> -10\%$, the inferiority assumption will be rejected.

- **Secondary Hypothesis 6 (Anti-rotavirus; GMC)**

Thirty days after the 6-month rotavirus vaccine administration, the GMCs of the serum IgA antibodies against the rotavirus in Group 1 are non-inferior to the GMCs in Group 2.

Null hypothesis (H0): $\text{GMC}(\text{rota, G1}) / \text{GMC}(\text{rota, G2}) \leq 2/3$

Alternative hypothesis (H1): $\text{GMC}(\text{rota, G1}) / \text{GMC}(\text{rota, G2}) > 2/3$

where $\text{GMC}(\text{rota, G1})$ and $\text{GMC}(\text{rota, G2})$ are the GMCs of the serum IgA antibodies against the rotavirus in Group 1 and Group 2, respectively. If the lower limit of the 2-sided 95% CI of the ratio of the GMCs from the 2 groups is $> 2/3$, the inferiority assumption will be rejected.

- **Secondary Hypothesis 7 (Anti-pertussis; GMC)**

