Table 5.7: Power estimates to reject the secondary hypotheses 1, 2, 3, 4, 5, 6, 7, and 8

Hypothesis #	Antigen	Endpoint	Non-inferiority margin	Estimated response*	Power (%)
1	Hepatitis B	% \geq 10 mIU/mL	10%	98%	>99.9
2	PRP	% \geq 0.15 μ g/mL	5%	91%	94.3
3	PRP	% \geq 1 μ g/mL	10%	81%	99.9
4	Polio type 1	% \geq 1:8	5%	\geq 99%	> 99.9
	Polio type 2	% \geq 1:8	5%	\geq 99%	> 99.9
	Polio type 3	% \geq 1:8	5%	\geq 99%	> 99.9
5	Rotavirus	% 3-fold rise	10%	95.2%	>99.9
6	Rotavirus	GMC	1.5	274.46 (323.52, 232.83) SD=2.00	>99.9
7	PT	GMC	1.5	65.0 (48.1, 87.7) SD=1.23	> 99.9
	FHA	GMC	1.5	91.4 (73.1, 114.3)	> 99.9

Hypothesis #	Antigen	Endpoint	Non-inferiority margin	Estimated response*	Power (%)
	PRN	GMC	1.5	SD=0.92	
				31.0 (19.9, 48.4) SD=1.83	>99.9
	FIM	GMC	1.5	173.5 (111.2, 269.1) SD=1.80	>99.9
8	Pneumococcal 1	GMC	2	3.5 (2.2 , 5.5) SD=1.10	> 99.9
	Pneumococcal 3	GMC	2	3.3 (1.9 , 6.0) SD=1.46	> 99.9
	Pneumococcal 4	GMC	2	2.0 (1.2 , 3.1) SD=1.07	> 99.9
	Pneumococcal 5	GMC	2	1.7 (1.2, 2.3) SD=0.74	> 99.9
	Pneumococcal 6A	GMC	2	4.8 (3.2, 7.3) SD=1.02	> 99.9
	Pneumococcal 6B	GMC	2	2.4 (1.1 ,5.3) SD=1.93	> 99.9
	Pneumococcal 7F	GMC	2	4.2 (2.5 , 7.0) SD=1.25	> 99.9
	Pneumococcal 9V	GMC	2	1.8 (1.3 , 2.6) SD=0.90	> 99.9
	Pneumococcal 14	GMC	2	8.3 (5.3 ,13.1) SD=1.11	> 99.9
	Pneumococcal 18C	GMC	2	2.3 (1.6 , 3.2) SD=0.81	> 99.9
	Pneumococcal 19A	GMC	2	1.6 (0.9 , 2.8) SD=1.37	> 99.9
	Pneumococcal 19F	GMC	2	3.8 (2.1, 6.7) SD=1.38	> 99.9
	Pneumococcal 23F	GMC	2	2.7 (1.6 ,4.7) SD=1.35	> 99.9

Hypothesis #	Antigen	Endpoint	Non-inferiority margin	Estimated response*	Power (%)
	Overall				94.2

Evaluable subjects: Group 1: n=1155; Group 2: n=577

*All estimates are from MET39, Group 2, 7-month or Group 1, 7-month data with the exception of rotavirus estimate from study V260-006 (NCT00090233) and study V419-005 (NCT01337167).

II. Second year evaluation at 30 days after the 12-month vaccinations

With 770 evaluable subjects in Subgroup 1a and 385 evaluable subjects in Subgroup 2a, the study will have around >99.9% power by using the Farrington and Manning's method to declare the non-inferiority of Subgroup 1a vs Subgroup 2a.

Table 5.8: Power estimates to reject the secondary hypotheses 9, 10, 11, 12 and 13

Hypothesis #	Antigen	Endpoint	Non-inferiority margin	Estimated response*	Power (%)
9	Measles	% \geq 255 mIU/mL	10%	95%	> 99.9
10	Mumps	% \geq 10 Mumps AbU/mL	10%	95%	> 99.9
11	Rubella	% \geq 10 IU/mL	10%	95%	> 99.9
12	Varicella	% \geq 5 gpELISA Ab units/mL	10%	95%	> 99.9

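### The pertussis and rotavirus GMC non-inferiority tests are valid but leave out the scheduled Day 0 concentration of the same antibody; adjusting for it is a cheap, modest gain in precision

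*SAP*

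**What the plan says.** SAP 5.1.2.2 handles all the GMC hypotheses (6 to 8 and 13) in one way: "the statistical methodology will be based on the use of the 2-sided 95% CI of difference in means of post-vaccination Log10 transformed concentrations". The formula that follows is the pooled-variance t interval for two independent samples, with no covariate. Under SAP 5.1.2.1, non-inferiority for Hypotheses 6 and 7 is judged by whether the "lower limit of the 2-sided 95% CI of the ratio of the GMCs from the 2 groups" exceeds 2/3. For Hypothesis 7 this must hold for each of PT, FHA, PRN and FIM. Protocol 12.1.2.1 and the synopsis state the same unadjusted method.

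In SAP 4.2.1.2, the rotavirus IgA assay and the multiplex diphtheria-tetanus-pertussis assay carry the same instruction: "This method will be performed on BL1 and BL2 collected from all groups". BL1 is the Day 0 sample, drawn before the first vaccination. The Day 0 values have other uses in the plan: the rotavirus 3-fold rise (Hypothesis 5), the descriptive 4-fold rise, and the pertussis vaccine response after dose 3 (SAP 4.4.1.4 and Table 5.4). Protocol 5.2.6 also records "Tdap vaccination received during pregnancy with the subject enrolled in the study and date of vaccination" to help interpret the data.

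BL1 is scheduled but not guaranteed. Protocol 5.1.4.1 (Visit 1) lets an infant continue when the draw fails. PPAS1 (SAP 5.2.2.1) names only the post-dose-3 sample, and SAP 5.4.2 does not impute missing serology.

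**The concern.** A pre-vaccination value of the outcome antibody is the obvious covariate for a comparison of post-vaccination means. It cannot be affected by the vaccine, so in a randomised comparison adjusting for it does not bias the group difference. It removes whatever outcome variance it explains, along with any chance imbalance at Day 0. The plan pays for the assay and uses the result elsewhere, but not in these two GMC comparisons.

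These are also the comparisons where precision is thinnest among the GMC tests. Rotavirus, PRN and FIM combine large SDs in SAP Table 5.7 (2.00, 1.83 and 1.80) with the tighter 1.5-fold margin. Pneumococcal 6B has an SD of 1.93 but a 2-fold margin. At stake is interval width and some protection against an unlucky baseline split, not the validity of the test.

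**Working it through.** **Inputs.** SAP Table 5.7: "Evaluable subjects: Group 1: n=1155; Group 2: n=577"; margin 1.5; SDs rotavirus 2.00, PT 1.23, FHA 0.92, PRN 1.83, FIM 1.80. Two-sided 95% interval, true GMC ratio of 1. The correlation r between log Day 0 and log post-dose-3 concentration is in neither document, so it is an assumption shown over a range.

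**Reproducing the plan's power.** Table 5.7 states more than 99.9% for each of these five tests and 94.2% overall for Hypotheses 1 to 8. It does not say which log base the SDs use.

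- SE = SD × √(1/1155 + 1/577) = SD × 0.05098.
- Power = Φ(log margin / SE − 1.96).
- Log2 SDs (margin log2 1.5 = 0.585): rotavirus SE 0.1020, power Φ(5.737 − 1.96) = 99.99%; the other four are higher. Multiplying by the binary powers (anti-PRP ≥ 0.15 µg/mL at 94.3% dominates) and the pneumococcal powers gives 94.2% overall. Both stated figures are reproduced.
- Natural-log SDs (margin ln 1.5 = 0.4055): rotavirus Φ(3.977 − 1.96) = 97.8%; PRN, SE 0.0933, Φ(4.346 − 1.96) = 99.1%; FIM, SE 0.0918, Φ(4.419 − 1.96) = 99.3%; PT and FHA above 99.9%. Overall 90.7%. The stated figures are not reproduced.
- Log10 SDs: powers from 41% to 96%, incompatible with the table.

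**Effect of adjustment.** The residual SD is SD × √(1 − r²), so the interval width is multiplied by √(1 − r²): 1.000, 0.995, 0.954 and 0.866 at r = 0, 0.1, 0.3 and 0.5. This holds for any log base. The equivalent gain in sample size is 1/(1 − r²) − 1: 10% at r = 0.3 and 33% at r = 0.5.

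| Power, natural-log SDs | r = 0 | r = 0.1 | r = 0.3 | r = 0.5 |
|---|---|---|---|---|
| Rotavirus | 97.8% | 97.9% | 98.6% | 99.6% |
| PRN | 99.1% | 99.2% | 99.5% | 99.9% |
| FIM | 99.3% | 99.3% | 99.6% | 99.9% |
| All five tests (product) | 96.3% | 96.5% | 97.8% | 99.4% |

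With log2 SDs every test starts at 99.99% or more, and no gain is visible.

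**Expected lower limit at a true ratio of 1, natural log:** exp(−1.96 × SE). Rotavirus moves from 0.819 to 0.826 (r = 0.3) or 0.841 (r = 0.5); PRN from 0.833 to 0.840 or 0.854. The margin is 0.667.

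**Missing Day 0 values.** If a share m of infants has no BL1 and is dropped, the variance changes by (1 − r²)/(1 − m). The gain is gone once m exceeds r²: 4% at r = 0.2, 9% at r = 0.3. A complete-case model could therefore do worse than the planned one.

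**The case against.** The strongest reply is that nothing is broken. The unadjusted interval is valid under randomisation, and planned power is very high on either plausible reading of the SDs. No expected conclusion changes: even the widest interval has an expected lower limit of 0.819 against 0.667. The weakest first-year test is anti-PRP ≥ 0.15 µg/mL at 94.3%, a binary endpoint for which the assay description lists no Day 0 sample, so adjustment cannot help it. The method is also written into the protocol, so changing it is more than a SAP edit. All of this stands, and it limits the point to efficiency.

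A reader might go further than the documents allow in four ways.

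- That the intervals are wider than they need to be. This holds only if r is not zero, and the documents report no r. Recording maternal Tdap suggests that the sponsor thinks maternal vaccination may matter, but reports no association with the post-dose-3 value.
- That Day 0 was measured in every infant. It is scheduled for every infant, but neither continued participation nor PPAS1 requires it.
- That the plan discards the Day 0 data. Only the GMC comparison omits them.
- That a power shortfall has been shown. 97.8% against a stated figure above 99.9% follows only from the natural-log reading; log2 reproduces the SAP. The unstated base is a separate matter that ANCOVA does not settle.

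What the reply does not answer is why a baseline the trial already collects should be left out of a pre-specified model when including it needs no new data.

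**Conclusion.** The point holds as a recommendation on efficiency. Hypotheses 6 and 7 use a valid but unadjusted comparison although a Day 0 value of the same antibody is scheduled in both groups. Adjustment would narrow the interval by 0%, 0.5%, 4.6% or 13.4% at assumed r of 0, 0.1, 0.3 or 0.5. The power gain is at most a few points for the five tests jointly under natural-log SDs (96.3% to 97.8% at r = 0.3, treating the tests as independent) and not visible under log2.

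The case is firmer for pertussis than for rotavirus. Neither document states an LLOQ for the rotavirus assay. If many Day 0 rotavirus values fall below it, they collapse to one substituted value and carry little information. The point does not extend to the pneumococcal hypotheses (8 and 13), which have no Day 0 assay.

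**What to change.** Before unblinding, pre-specify for Hypothesis 7 an ANCOVA of log10 post-dose-3 concentration on vaccine group and log10 Day 0 concentration, one model per antigen. Set Day 0 values below the LLOQ to LLOQ/2, as SAP 4.4.1.1 already provides. Apply the same model to Hypothesis 6 once the rotavirus LLOQ is stated. Keep infants without BL1 by a missing-indicator term, so that no PPAS1 infant is lost. Back-transform the adjusted difference and its 95% interval to the GMC ratio, test it against 2/3, and report the unadjusted ratio as supportive.

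Record the change in SAP 5.8 and align protocol 12.1.2.1 and the synopsis, which carry the unadjusted method.

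The cost is one model per antigen, a rule for missing BL1, and a documented departure from the protocol's stated method. No new samples, visits or assays are needed. The timing matters: an adjustment chosen after group results are known would look data-driven.

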5.6 Determination of Sample Size and Power Calculation

Calculation of Sample Size:

Approximately 2628 subjects will be enrolled. An estimated maximum of up to 34.1% non-evaluable subjects will result in approximately 1732 subjects in the PPAS available for immunogenicity analyses. Group 1 will have 1155 evaluable subjects and Group 2 will have 577 evaluable subjects.

In case of unexpected situation or any study hold resulting in an unexpected number of unevaluable subjects, total sample size may be increased to replace withdrawn, or unevaluable subjects.

For the Primary Objective 1 (after the 4th dose):

With 770 evaluable subjects in Subgroup 1a and 385 evaluable subjects in Subgroup 2a, the study will have around 98.4% power by using the Farrington and Manning's method to declare the non-inferiority of Subgroup 1a vs Subgroup 2a.

For the Primary Objective 2 (after the 3rd dose):

With 1155 evaluable subjects in Group 1 and 577 evaluable subjects in Group 2, the study will have around 98.8% power by using the Farrington and Manning's method to declare the non-inferiority of Group 1 vs Group 2.

Co-primary Objectives:

The study will have around 97.2% overall power by using the Farrington and Manning's method to declare the non-inferiority for co-primary objectives.

Table 5.6: Power estimates to reject the primary hypotheses

Primary #	Antigen	Endpoint	Non-inferiority margin	Estimated response*	Power (%)
Primary 1 (after 4th dose)	A	Seroresponse Rate	10%	80%	98.4
	C	Seroresponse Rate	10%	90%	99.98
	Y	Seroresponse Rate	10%	90%	99.98
	W	Seroresponse Rate	10%	90%	99.98
Primary 2 (after 3rd dose)	A	% \geq 1:8	10%	70%	99.2
	C	% \geq 1:8	10%	80%	99.9
	Y	% \geq 1:8	10%	80%	99.9
	W	% \geq 1:8	10%	80%	99.9
Overall					97.2

Note: Evaluable subjects for Primary 1: Subgroup 1a: n = 770 subjects; Subgroup 2a: n = 385 subjects

Evaluable subjects for Primary 2: Group 1: n = 1155 subjects; Group2: n = 577 subjects

*Estimated responses are based on results observed in MENVEO® V59_33 (NCT01000311) and in study MET39 (Group 1 TetraMen-T 2, 4, 6, 12 months).

For the Secondary Objectives:

I. First year evaluation at 30 days after the 6-month vaccinations (after the 3rd dose)

With 1155 evaluable subjects in Group 1 and 577 evaluable subjects in Group 2, the study will have around 94.2% power by using the Farrington and Manning's method to declare the non-inferiority of Group 1 vs Group 2.

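### The GMC-ratio intervals for secondary hypotheses 6, 7, 8 and 13 pool the variances under 2:1 allocation, so they hold their 95% level only if the two groups' SDs are equal; a Welch interval removes that condition at no cost.

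*SAP*

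**What the plan says.** SAP 5.1.2.2 introduces the method with "For each of the non-inferiority hypotheses (hypothesis 6 to 8 and 13) using the GMC ratios" and says that it "will be based on the use of the 2-sided 95% CI of difference in means of post-vaccination Log10 transformed concentrations". The interval given there is the difference in mean log10 concentration, plus or minus a t quantile on ni + nj − 2 degrees of freedom times S·sqrt(1/ni + 1/nj), where S squared "is the pooled sample variance". The section states normality of the log10 data. It states no equal-variance assumption, no variance check and no unequal-variance alternative.

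SAP 3.1 says that infants "will be randomized 2:1 to the following 2 groups", and then "Each group will be further randomized 2:1 in 2 subgroups". Group 1 vs Group 2 (hypotheses 6 to 8) and Subgroup 1a vs Subgroup 2a (hypothesis 13) are therefore both 2:1. SAP 5.6 confirms the sizes: "With 1155 evaluable subjects in Group 1 and 577 evaluable subjects in Group 2" and "With 770 evaluable subjects in Subgroup 1a and 385 evaluable subjects in Subgroup 2a".

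Protocol 12.1.2.1 asks only for a two-sided 95% interval for the difference in log10 means under a normal approximation. It does not call for pooling.

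**The concern.** The pooled t interval tolerates unequal variances when the arms are the same size. At 2:1 it does not. The larger group dominates the pooled variance, while the smaller group contributes most of the true variance of the difference. If the SDs differ, the pooled standard error converges to the wrong value. The central limit theorem protects against non-normal data but not against this.

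The interval decides formal non-inferiority tests under secondary objective 1: rotavirus (1), pertussis (4 antigens) and pneumococcal serotypes (13 at each of two time points), which makes 31 comparisons. If the smaller MENVEO group had the larger SD, the interval would be too narrow and false non-inferiority more likely than 2.5%. If the MenACYW group had the larger SD, the interval would be too wide and some power would be lost.

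**Working it through.** **Inputs.** From SAP 5.6, n1/n2 = 1155/577 (hypotheses 6 to 8) and 770/385 (hypothesis 13). From SAP 5.1.2.1, the margins are 2/3 (hypotheses 6 and 7) and 1/2 (hypotheses 8 and 13). From SAP 5.1.2.2, the interval is two-sided 95%, so the test is one-sided at 2.5%. The SD ratio r = SD(Group 2)/SD(Group 1) is not in the documents; it is assumed and varied. It does not depend on the base of the logarithm.

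**Formula.** Take SD(Group 1) = 1.
- Pooled variance of the difference: Sp²·(1/n1 + 1/n2), with Sp² = [(n1 − 1) + (n2 − 1)r²]/(n1 + n2 − 2).
- True variance: 1/n1 + r²/n2.
- q = pooled SE / true SE. The one-sided error at the margin is 1 − Φ(1.96·q).

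At 2:1, q² is approximately (1 + r²/2)/(1/2 + r²). No sample size appears, and it equals 1 only at r = 1.

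**Nominal level.** At r = 1, q = 1 and the error is 2.50%, so the SAP's 95% level is reproduced when the SDs are equal.

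**Worked case, r = 1.25, 1155/577.** Sp² = (1154 + 576 × 1.5625)/1730 = 1.1873. Pooled SE = sqrt[1.1873 × (1/1155 + 1/577)] = 0.05555. True SE = sqrt(1/1155 + 1.5625/577) = 0.05978. q = 0.929, and the error is 1 − Φ(1.821) = 3.4%.

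| r | q | One-sided error | Two-sided coverage |
|---|---|---|---|
| 0.8 | 1.076 | 1.75% | 96.5% |
| 0.9 | 1.036 | 2.1% | 95.8% |
| 1.0 | 1.000 | 2.5% | 95.0% |
| 1.1 | 0.969 | 2.9% | 94.2% |
| 1.25 | 0.929 | 3.4% | 93.1% |
| 1.5 | 0.879 | 4.25% | 91.5% |

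The results for 770/385 are the same to the precision shown. With 100 times the sample (115500/57700) the errors at 0.8, 1.1, 1.25 and 1.5 are 1.75%, 2.88%, 3.43% and 4.25%. At 1:1 the error is nominal at every ratio, so the cause is pooling combined with unequal allocation. Simulation of the SAP's interval (400,000 trials per setting, 1155/577) gives 1.73%, 2.86%, 3.40% and 4.21% at the same four ratios.

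**Effect on a lower limit.** Take the rotavirus SD of 2.00 from SAP Table 5.7 as the Group 1 SD. The natural-log scale is inferred, because the tabulated pertussis SDs match their intervals on that scale. With an observed GMC ratio of 1 and a margin of 0.667:
- r = 1.1: pooled SE 0.1055, limit exp(−1.96 × 0.1055) = 0.813; unpooled SE 0.1089, limit 0.808.
- r = 1.25: pooled SE 0.1111, limit 0.804; unpooled SE 0.1196, limit 0.791.

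**Welch interval.** Its simulated one-sided error is 2.46% to 2.55% for r from 0.8 to 1.5 at both sample sizes. Power when the true GMCs are equal, with the tabulated SD as the Group 1 SD:

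| r | PRN, pooled / Welch | Rotavirus, pooled / Welch |
|---|---|---|
| 0.8 | 99.79% / 99.87% | 99.3% / 99.5% |
| 1.0 | 99.1% / 99.1% | 97.9% / 97.9% |
| 1.25 | 97.0% / 95.9% | 94.1% / 92.3% |

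The gap at 1.25 arises because the pooled interval is too narrow there.

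**The case against.** The pooled t interval is a conventional, fully pre-specified method that fits the protocol's wording, and it is exact if the SDs are equal and the log data normal. Nothing in the documents shows that they are unequal. The power tables in SAP 5.6 carry one SD per antigen, taken from earlier studies. Both groups receive the same RotaTeq, Pentacel and Prevnar 13, tested in blinded assays, and no meningococcal titre is tested with this interval. The different carrier proteins (tetanus toxoid and CRM197) make an effect on the spread of co-administered antigens possible but do not demonstrate one. Nor does the wider age window for the fourth Prevnar 13 dose in Group 1 (12 to 15 months, against 12 months in Group 2). Neither fact settles the direction.

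Much of this stands. It limits the weight of the point, but it does not answer the algebra: the plan relies on equal variances without saying so, and sample size does not remove that reliance.

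A reader might infer that 31 comparisons run at an inflated error of 3% to 4%. The documents do not support that. The ratios behind those figures are stress cases, the error may equally be conservative, and hypotheses 7, 8 and 13 succeed only if every antigen or serotype passes. False success for each of those three therefore cannot exceed the error of a single component test. Decisions are also seldom at risk: at a ratio of 1.25 the rotavirus limit moves by less than 2% (0.804 to 0.791).

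**Conclusion.** The point holds conditionally. Under 2:1 allocation the specified interval keeps its 95% level only if the two groups' SDs are equal, and more subjects would not change that. The one-sided error is about 2.1% to 2.9% for SD ratios of 0.9 to 1.1. Outside that range, as stress cases, it is 1.75% at 0.8, 3.4% at 1.25 and 4.25% at 1.5. These figures rest on assumed ratios and on approximate normality of the log concentrations; the algebra itself is certain.

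The scope is secondary hypotheses 6, 7, 8 and 13. The two primary hypotheses and every percentage endpoint use the Wilson score interval (SAP 5.1.1.2 and 5.1.2.2) and are untouched. Rotavirus is the most exposed because hypothesis 6 rests on a single test and has the largest tabulated SD. The pneumococcal tests have so much power under true equality that the choice of interval would rarely alter their result. The point does not show that any conclusion of this trial would be wrong. It identifies an avoidable assumption, and removing it is a free improvement.

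**What to change.** In SAP 5.1.2.2, for hypotheses 6 to 8 and 13, replace S·sqrt(1/ni + 1/nj) on ni + nj − 2 degrees of freedom by sqrt(Si²/ni + Sj²/nj) with Satterthwaite degrees of freedom (the Welch interval), and delete the pooled-variance definition. Margins, hypotheses and sample size stay as they are, and the protocol's normal-approximation wording already accommodates the change. The cost is one line of SAP text and output that SAS produces as standard.
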